8 STATISTICAL ANALYSIS FOR EXPLORATORY OBJECTIVES

8.1 Overview of Exploratory Objectives

The exploratory objectives are as follows:

Exploratory objective 1: To assess whether VE against primary endpoint 1 and 2 depends on genotypic characteristics of the malaria parasites, based on longitudinal monthly and other unscheduled sampling.

Exploratory objective 2: To study whether prior infection or vaccination has a relationship to subsequent infection by measuring the molecular Force of Infection (mol[FOI]) determining the relationship between (mol)FOI and subsequent malaria infection risk.

Exploratory objective 3: To determine whether prior infection by a particular parasite genotype, not necessarily the vaccine strain, reduces the likelihood of re-infection by a parasite with the same genotype.

Given that the exploratory analyses must deal with the diversity of malaria infections, we first describe a section of how we plan to characterize AA sequence features and within-infection malaria diversity. Subsequent sections describe how the analyses to meet the exploratory objectives account for that characterization.

8.2 Structuring AA Sequence Features for Sieve Analysis (Exploratory Objective 1)

The exploratory objective 1 involves evaluating whether and how the various efficacy and relative efficacy comparisons, described in Table 2 plus the additional comparison of active arms GP2–GP4 pooled vs. the control arm, for primary endpoints 1 and 2 depend on different AA sequence features pre-specified in a treatment-blinded manner. All features will be calculated using aligned translated AA sequences of the CS C-terminus and SERA2 amplicons, obtained after application of the standardized error filtration process (Early et al., 2019) to the underlying nucleotide sequence data measured on an Illumina platform. We will consider two categories of features:

- (i) features that are characteristics at the haplotype level, and
- (ii) features that are characteristics at the sample level.

Category (i) constitutes the same set of features that were analyzed in the Phase 3 trial sieve analysis and published in Neafsey et al. (2015) and Benkeser, Juraska and Gilbert (2020). These features are as follows:

- a) AA residue match vs. mismatch to the 3D7 vaccine strain in the full CS C-terminus amplicon;
- b) AA residue match vs. mismatch to the 3D7 vaccine strain in each of the following four haplotypic regions in the CS C-terminus: Th2R, Th3R, DV10, and the LD haplotype (a union of specified positions in Th2R and Th3R in linkage disequilibrium);
- c) AA residue match vs. mismatch to the 3D7 vaccine strain at individual polymorphic AA positions in the CS C-terminus;
- d) Hamming distance to the 3D7 vaccine strain based on the full CS C-terminus amplicon as well as in each of the haplotypic regions in (b).

In addition, sieve analyses for (a), (c), and the full amplicon in (d) will be repeated for the SERA2 amplicon. This analysis serves as a control for the analysis of the CS C-terminus amplicon, given that SERA2 is not included in the vaccine, and hence we assume that there should be no sieve effects in SERA2.

The novelty in the analysis of the same features as in the Phase 3 trial sieve analysis is twofold: it will characterize sieve effects pertaining to the fractional dose regimens, and it will characterize feature-specific efficacy and relative efficacy against primary endpoints 1 and 2.

Features in category (ii) aim to describe within-host *P. falciparum* population complexity using multiple different sample-level complexity indices to capture different aspects of the proteomic diversity and to subsequently study variations in vaccine efficacy and relative efficacy with the selected complexity measures. With the exception of COI, all other complexity indices disregarding the vaccine strain will be calculated separately for the CS C-terminus and SERA2 loci as the sequencing technology does not provide requisite data to concatenate sequences from the two amplicons. The indices, specified below, were down-selected from a large pool of indices described in Gregori et al. (2016). The down-selection was based on a combination of the authors' recommendations and results from an exploratory study, performed by the Fred Hutch statistics group, of statistical properties of all Gregori et al. indices and their inter-relatedness using CS C-terminus amplicon AA sequence data from clinical malaria and Month 20 cross-sectional parasite positivity cases among participants aged 5-17 months in the MAL-066 trial that were also analyzed in Neafsey et al. (2015).

The following complexity indices (i.e., estimators) in category (ii) will be calculated in each sample, separately for the CS C-terminus and SERA2 amplicon:

- e) Hill numbers (Hill, 1973), $H(q)$, of orders $q = 0, 1$, and 2 , where $H(0)$ is the number of distinct haplotypes observed in the sample, $H(1)$ is undefined but its limit as q tends to 1 is the exponential of Shannon entropy, and $H(2)$ is the inverse of the Simpson index defined as the probability that two sequence reads drawn at random in a given sample belong to the same haplotype;
- f) the standardized number of segregating AA positions, S/a_1 , where S is the number of segregating positions, and $a_1 = \sum_{i=1}^{n-1} 1/i$, where n is the number of reads in a given sample; and
- g) the mean Hamming distance to the 3D7 strain with equally weighted haplotypes.

In addition to (e)-(g), we will analyze variation in efficacy and relative efficacy by

- h) COI,

which pools information from both amplicons and equals the maximum of the Hill numbers $H(0)$ for CS C-terminus and SERA2.

Indices (e), (f) and (h) disregard the 3D7 reference sequence, whereas index (g) accounts for the 3D7 sequence (which, for CS C-terminus, was the vaccine insert). The mean pairwise Hamming distance is not considered for analysis because we anticipate that a large portion of the first new infections will have COI = 1, and therefore zero mean pairwise Hamming distance. Indices (e)-(g) will be calculated using the Fred Hutch's internal R package *divIndex*.

For analyses in pursuit of the exploratory objective 1, for each AA sequence feature in both categories (i) and (ii), we will calculate the value(s) of the feature in the sample associated with the first molecular detection of a new infection (i.e., primary endpoint 1) as well as pooling all samples associated with all molecular detections of a new infection in a given participant within the studied follow-up period, unless data are missing for these calculations. For category (i) features, a value will be calculated, if possible, for each haplotype. For each category (ii) feature, we will generate scatter-box-violin plots of the observed values of the feature by study group. Furthermore, we will generate Hill number profiles for q in $[0, \infty]$ by study group, where, for a given q , each study group-specific curve will show the mean Hill number across all samples in this group associated with the first new infection.

We expect that 20% or more of primary endpoint 1 cases will have missing haplotype data for one amplicon. This is a result of the fact that measuring at least 1 haplotype (with ≥ 50 reads) for one amplicon and none for the other is sufficient to register the event as primary endpoint 1. We will use missing-data versions of sieve analysis methods to account for the missing haplotype data.

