Associated with each sample with molecular detection of malaria infection is the complexity of infection (COI), defined as the maximum of (i) the number of unique haplotypes for the CS C-terminus amplicon, and (ii) the number of unique haplotypes for the SERA2 amplicon in the sample. It is expected that the cause of $n = COI > 1$ is multiple distinct malaria infections; thus, COI itself is one estimate of the number of new molecularly confirmed malaria infections that have occurred up to the time of the given sample. However, simultaneous super-infection is possible, and some new malaria infections could be undetected if enough time elapses between infection and sampling, or if antimalarial treatment clears an infection.

The following paragraphs provides more detail on the definition of a new malaria infection.

Malaria infection

A *P. falciparum* infection is defined as amplicon nucleotide sequence-based parasite positive status defined as detection of at least one haplotype supported by at least 50 nucleotide sequence reads and 1% of total reads for at least one of the two amplicons.

New malaria infection

As there is no guarantee of complete clearance of infections, a new infection may originate from a post-enrollment sample that goes from negative to positive, or from a post-enrollment sample that contains a new haplotype that was not previously observed in several previous samples from the same participant. A new infection for the primary objective is defined as at least one of the haplotypes in the post-enrollment sample not being detected in the previous three samples drawn from the same participant regardless of the visit type (scheduled or unscheduled). An exception is made if a haplotype is detected in the first post-enrollment sample not collected on the day of enrollment, in which case it counts as a new infection if the same haplotype was not detected in the single sample from the enrollment visit. Haplotype detection requires observation of at least 50 reads and 1% of total reads supporting the haplotype within a sample. Note that a molecularly confirmed infection in a sample from the enrollment visit does not count as a new infection because the sample was collected prior to administration of the first dose, and therefore the sample should not contribute to measuring the vaccine effect. A molecularly confirmed infection in a sample from an unscheduled visit that occurred on the day of enrollment does not count as a new

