For the haplotype-specific AA sequence features (a)–(c) that are categorical, a screening process is needed to determine which features have a large enough representation in the data set, and enough variability, to make possible sieve analysis. A subset of the features in (a)–(c) will be selected for sieve analysis, defined as follows: Two screened-in feature sets are defined, one for the analysis of the first new infection, and one for longitudinal data analysis including new haplotypes (i.e., not observed in the participant's previous new infections) from all new infections in the ATP cohort with follow-up through 12 months post-Dose 3 (see Section 8.4.1 for the sieve analysis cohort and follow-up period), relevant for primary endpoint 2 of this objective and for exploratory objective 3. We first describe the former screen. For each feature (i.e., a 3D7 match/mismatch in a specific haplotypic region, or an AA residue 3D7 match/mismatch at a specific AA position), the frequencies of the possible values of each feature (0 or 1 for a match/mismatch feature) among all first new infection endpoint cases (pooling over all treatment arms included in a comparison) will be tabulated (number of primary endpoint 1 cases with a given feature value / number of primary endpoint 1 cases). Feature values with representation from at least 30 participants, pooling over all treatment arms included in a comparison, will be screened-in for data analysis of vaccine efficacy or relative vaccine efficacy against primary endpoint 1 with the given feature value. In addition, only features for which there is enough representation from at least 30 participants for each level of the feature (e.g., for both 3D7 match and mismatch) will be screened-in for sieve analysis of differential vaccine efficacy or relative vaccine efficacy across different feature levels associated with the primary endpoint 1 sample. The number 30 may be altered based on this descriptive analysis, which is valid because the screening procedure itself is blinded to randomization arm (albeit the selection of arms in a comparison is unblinded).

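### Endpoint 1 sieve features are taken from every haplotype in the first-new-infection sample, so strains carried in from before the window can be analysed as the breakthrough genotype and pull sieve effects toward null

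*SAP*

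**What the plan says.** Section 5.1.1 of the SAP classes a sample as a new infection on the strength of "at least one of the haplotypes in the post-enrollment sample not being detected in the previous three samples drawn from the same participant". The other haplotypes in the sample need not be new, and the same section accepts that infections may not clear completely.

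Section 8.2 takes the endpoint 1 features from the whole of that sample: "we will calculate the value(s) of the feature in the sample associated with the first molecular detection of a new infection". It adds: "For category (i) features, a value will be calculated, if possible, for each haplotype". Sections 8.4 and 8.4.2 then use methods that assume one haplotype per case, with multiple outputation for features (a)-(d). No sentence limits the draw to new haplotypes.

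The sample-level features behave in the same way. H(0) "is the number of distinct haplotypes observed in the sample", and COI is the larger of the two amplicons' H(0). Section 5.1.1 reads COI as cumulative: "COI itself is one estimate of the number of new molecularly confirmed malaria infections that have occurred up to the time of the given sample".

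A limit to new haplotypes is written once, in Section 8.3, for the all-infections screen, which covers "new haplotypes (i.e., not observed in the participant's previous new infections) from all new infections". The endpoint 1 screen in the same paragraph has no such limit.

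**The concern.** A strain-specific hazard analysis needs the genotype of the event being counted. A strain acquired before the window carries no information about what the vaccine let through during it. If outputation draws such a strain, the vaccine-arm genotype mix moves back toward the circulating mix, and a real difference in VE between matched and mismatched parasites looks smaller.

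The plan's safeguard is the expectation in Section 8.4 that a first new infection will usually have a COI of 1. That concerns how many strains a new infection brings, not how many the child already holds.

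A null result here has consequences. SAP Section 9.3 motivates further post-hoc work by a finding that preferential blocking of vaccine-matched infections does not account for the sieve effect on clinical malaria. The SERA2 control analysis cannot reveal the problem, because a diluted null is still a null.

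**Working it through.** **Can old strains enter?** Yes.
- The sieve cohort is ATP (Section 8.4.1). Section 3 requires only that the child be at risk at 14 days post-Dose 3. Section 9.4.1 tabulates ATP children who are baseline positive or have M2-FOI above zero.
- Section 9.4.2.1.1 expects hundreds of extra baseline-negative matches from the second and third match per baseline-positive child. Reading that as at least 200 over two matches gives 100 or more baseline positives among at most 4 x 300 = 1,200 children, or about 8% or more.
- At the first event in a window, no earlier in-window sample held a new haplotype. Any haplotype that is not new therefore traces back to a sample taken before the window.

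**Plan's own figure.** None exists. The documents give no carriage rate, persistence, treatment rate or expected COI distribution for this analysis.

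**Dilution for a given carry-over share c.**
- Benchmark: the hazard-ratio VEs in Protocol Section 2.2, 62.7% (match) and 54.2% (mismatch). Section 8.4.2 plans a hazard-ratio analysis for (a)-(c). These VEs concern clinical malaria in phase 3, so they serve only as a worked effect.
- Ratio of hazard ratios: 0.373/0.458 = 0.814.
- Assumed match frequency p = 10%. Vaccine-arm match share among new strains: p_v = 0.10 x 0.373 / (0.10 x 0.373 + 0.90 x 0.458) = 0.0373/0.4495 = 0.0830.
- Observed share: (1 - c) x p_v + c x p. Observed ratio: odds of that share divided by the odds of p, 0.10/0.90.
- Events needed for the same power grow by 1/(fraction of log effect kept) squared.

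| c | observed share | ratio | log effect kept | events needed |
|---|---|---|---|---|
| 0 | 0.0830 | 0.814 | 100% | 1.00x |
| 4% | 0.0837 | 0.822 | 96% | 1.09x |
| 7% | 0.0842 | 0.827 | 92% | 1.17x |
| 10% | 0.0847 | 0.833 | 89% | 1.26x |
| 20% | 0.0864 | 0.851 | 79% | 1.62x |

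With p at 5% or 20% the ratios change by less than 0.001. Event times and the overall hazard ratio do not change.

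**How large might c be?** Simulation, 8,000 children per arm, with these assumptions:
- 0.5 control infections per month. Protocol Section 2.4.3 expects 10 or more infections in many children; 10 over 20 months is 0.5.
- Vaccine rate ratio 0.6 throughout, 10% baseline carriage, each infection a distinct haplotype.
- Monthly samples, full detection, and the three-sample rule.
- Treatment, where present, clears all strains half a month after the treated infection.

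The share is the chance that an outputation draw is an old strain, control vs vaccine:

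| Window, persistence | no treatment | 50% of infections treated, both arms | 50% control, 30% vaccine |
|---|---|---|---|
| M2.5-14, 2 months | 9.6% vs 4.9% | 2.7% vs 1.8% | 2.8% vs 2.6% |
| M7.5-19, 2 months | 13.4% vs 6.8% | 3.1% vs 1.9% | 3.1% vs 3.5% |
| M2.5-14, 4 months | 18.5% vs 10.8% | 5.5% vs 3.8% | 5.4% vs 6.5% |
| M7.5-19, 4 months | 31.5% vs 18.8% | 7.2% vs 5.1% | 7.0% vs 9.1% |

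The vaccine-arm range is 1.8-18.8%. With 80% detection, no treatment and no vaccine effect before the window, the last row's vaccine share is about 22-23%. A wider grid without treatment (0.1-0.5 per month, 2-6 months' persistence) gave 0.6-34%.

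**COI, M7.5-19, 2 months.** Without treatment, the whole-sample means are 1.54 vs 1.27 (difference 0.27), against 1.21 vs 1.11 on new haplotypes (0.10). With 50% vs 30% treatment they are 1.23 vs 1.18 and 1.16 vs 1.11, a difference of 0.05 on either measure.

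**The case against.** Several counter-arguments carry weight.

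- **COI.** A reader might infer that the plan manufactures an arm difference in COI, with controls carrying more old strains. The documents do not support that sign. SAP Section 7.1 says treatment may be less frequent in vaccine arms, and the simulation shows that such a difference can equalise or reverse carry-over. Features (e)-(h) are also sample-level by design.
- **Size.** The table treats every carried-over strain as unfiltered. Strains acquired after Dose 1 may be partly filtered already, so the ratios are upper bounds on dilution for a given share.
- **Endpoint 2.** A reader might extend the point to X_cf in Section 8.4.4. That quantity is already tied to the sequences of each new infection.
- **A plain filter has a cost.** The two amplicons cannot be concatenated (Section 8.2), and each locus has at least four haplotypes at 10% or more at most phase 3 sites (Protocol Section 2.4.3). A new strain may be flagged by SERA2 alone while sharing its CS haplotype with an older one. Filtering on CS would then lose or misstate its genotype, and would preferentially remove common haplotypes.

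None of this removes the central point: as written, the outputation draw for (a)-(d) includes strains that are not the event.

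**Conclusion.** The concern holds for haplotype-level features (a)-(d) at endpoint 1. The direction, toward null, follows from the text, provided that persistence does not itself depend on 3D7 match. The size is uncertain: about 2-19% carry-over in the vaccine arms under the stated assumptions, moving a ratio of 0.814 to no more than about 0.85. At low transmission with short persistence it is negligible.

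For COI and the complexity indices the supportable statement is narrower. They mix old and new strains, so an arm difference cannot be read as an effect on breakthrough complexity, and the sign of the distortion is unknown. Only exploratory objective 1 is affected; the primary VE estimates do not use these features.

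**What to change.** - In Sections 8.2 and 8.4.2, compute (a)-(d) for endpoint 1, and run multiple outputation, only over haplotypes of the analysed amplicon that are new under Section 5.1.1.
- Where the event is new only at the other amplicon, use all haplotypes of the analysed amplicon in that sample; as a sensitivity analysis, treat the genotype as missing.
- Report the whole-sample version alongside, and label the change post hoc, since Section 9.3 shows that results are already known.
- Keep (e)-(h) as sample-level measures, and add a new-haplotype-only version of COI and H(0) as a sensitivity analysis.

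The cost is SAP wording and a filter on flags already derived to define the endpoint, fewer haplotypes per case, and the fallback rule. Because detection is intermittent, an old strain missed in three consecutive samples will still pass as new, so the filter removes most carry-over but not all. If the analysis code already restricts to new haplotypes, one sentence in Section 8.2 settles the main point.

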8.3 Pre-screening of CS C-terminus and SERA2 Sequence Features

To maximize statistical power to detect sieve effects, a pre-specified screening process is used to select a subset of the features listed in Section 8.2 to include in sieve analyses addressing exploratory objective 1. The screening procedure, described below, is performed separately for each comparison, pooling over all treatment arms included in the comparison (i.e., blinded to individual treatments included in the comparison). However, to identify the treatment arms included in the comparison, the treatment assignments must be available. The treatment comparisons considered for exploratory objective 1 are listed in Table 2, in addition to the comparison of active arms GP2–GP4 pooled vs. the control arm. The screening procedure will be conducted separately for each study site-specific analysis and for the study site-pooled analysis.

For the haplotype-specific AA sequence features (a)–(c) that are categorical, a screening process is needed to determine which features have a large enough representation in the data set, and enough variability, to make possible sieve analysis. A subset of the features in (a)–(c) will be selected for sieve analysis, defined as follows: Two screened-in feature sets are defined, one for the analysis of the first new infection, and one for longitudinal data analysis including new haplotypes (i.e., not observed in the participant's previous new infections) from all new infections in the ATP cohort with follow-up through 12 months post-Dose 3 (see Section 8.4.1 for the sieve analysis cohort and follow-up period), relevant for primary endpoint 2 of this objective and for exploratory objective 3. We first describe the former screen. For each feature (i.e., a 3D7 match/mismatch in a specific haplotypic region, or an AA residue 3D7 match/mismatch at a specific AA position), the frequencies of the possible values of each feature (0 or 1 for a match/mismatch feature) among all first new infection endpoint cases (pooling over all treatment arms included in a comparison) will be tabulated (number of primary endpoint 1 cases with a given feature value / number of primary endpoint 1 cases). Feature values with representation from at least 30 participants, pooling over all treatment arms included in a comparison, will be screened-in for data analysis of vaccine efficacy or relative vaccine efficacy against primary endpoint 1 with the given feature value. In addition, only features for which there is enough representation from at least 30 participants for each level of the feature (e.g., for both 3D7 match and mismatch) will be screened-in for sieve analysis of differential vaccine efficacy or relative vaccine efficacy across different feature levels associated with the primary endpoint 1 sample. The number 30 may be altered based on this descriptive analysis, which is valid because the screening procedure itself is blinded to randomization arm (albeit the selection of arms in a comparison is unblinded).

Similarly, for longitudinal data analysis including all new infections during M0-20, the following screen is used: For each feature in (a)–(c), the frequencies of the possible values of each feature among all new infection endpoint cases (pooling over all treatment arms included in a comparison) will be tabulated (number of primary endpoint 2 cases with a given feature value / number of primary endpoint 2 cases). Parallel to the above, feature values with representation from at least 50 participants, pooling over all treatment arms included in a comparison, will be screened-in for data analysis of vaccine efficacy against primary endpoint 2 with the given feature value, and only features for which there is enough representation from at least 50 participants for each level of the feature will be screened-in for primary endpoint 2 exploratory objective 1

and 3 sieve analyses. As above, the number 50 may be altered based on this descriptive analysis, which is valid because the screening procedure itself is blinded to randomization arm (albeit the selection of arms in a comparison is unblinded).

8.4 Analysis of Exploratory Objective 1

Exploratory objective 1 is approached in two ways: first, for primary endpoint 1, and, second, for primary endpoint 2, for which the issue of COI is treated differently. For primary endpoint 1, it is expected that the first new malaria infection will usually have COI = 1 (under the premise that most new infections are with a single haplotype), or occasionally COI = 2 or 3 if co-infection from the same mosquito sometimes occurs or multiple mosquito transmission events occur between longitudinal monthly blood samples. Because COI is expected to be low for primary endpoint 1, for haplotype-specific AA sequence features (a)–(d), sieve analysis methods that assume only one haplotype will be used, and exhaustive or Monte Carlo multiple outputation applied, similar to what was done in Neafsey et al. (2015). For sample-specific sequence features (e)–(h), the employed sieve analysis methods will not require to be augmented with multiple outputation.

In contrast, for primary endpoint 2, COI by the end of a given follow-up period may be quite large and is essentially the same concept as primary endpoint 2 itself in being closely related to the number of new malaria infections by a given time point. Therefore sieve analyses of primary endpoint 2 treat COI as a key issue, and the “active surveillance” versions of the Follmann and Huang (2018) methods are one set of methods that apply, where the “terminal event” is defined as the last new malaria infection event during the specified follow-up period.

The following paragraphs describe the exploratory statistical analyses that are planned of the AA sequence features described above.

